**EXHIBIT D.8.A. Preliminary Burnout Model for Power Calculations**

		Coefficient (95% CI)	
	Empty	Unadjusted Model	Adjusted Model

Model			
Program Strata (ref: Stratum 1)			
Stratum 2	---	2.510 (1.643-3.377)	2.134 (1.261-3.007)
Stratum 3	---	3.442 (2.575-4.309)	3.076 (2.202-3.951)
Stratum 4	---	6.258 (5.384-7.131)	5.598 (4.719-6.477)
Stratum 5	---	0.273 (-0.885-1.430)	---
Female (ref: male)	---	---	2.064 (1.544-2.583)
PGY level (ref: PGY1)			
PGY2	---	---	0.479 (-0.276-1.233)
PGY3	---	---	-0.101 (-0.874-0.673)
PGY4	---	---	-0.607 (-1.393-0.179)
PGY5	---	---	-0.548 (-1.350-0.253)
Relationship status (ref: not in relationship)			
Married	---	---	0.265 (-0.408-0.938)
In a relationship	---	---	0.965 (0.279-1.651)
Divorced/widowed	---	---	-0.318 (-2.203-1.566)
Non-white (ref: white)	---	---	-1.512 (-2.056- -0.968)
Geographic region (ref: Northeast)			
Southeast	---	---	0.124 (-0.690-0.939)
Midwest	---	---	0.307 (-0.484-1.098)
Southwest	---	---	0.033 (-0.958-1.023)
West	---	---	0.064 (-0.299-1.582)
Program type			
Community	---	---	-0.069 (-0.810-0.672)
Military	---	---	-0.322 (-1.985-1.341)
Program size	---	---	0.125 (-0.056-0.306)
Constant	49.753 (49.356-50.150)	46.970 (46.325-47.615)	45.933 (44.461-47.405)
Variance components			
Level-2	7.413 (5.627-9.767)	1.821 (1.010-3.285)	1.010 (0.417-2.446)
Level-1	83.483 (80.459-86.622)	83.721 (80.686-86.870)	81.485 (78.303-84.795)
Intraclass correlation	0.082	0.021	0.012
N residents	5962	5962	5075
N programs	300	300	237
Likelihood ratio test vs. linear model (x2)	172.20	18.29	6.94
P value	P<0.001	P<0.001	P=0.004
Data: 2019 (version 2) and 2018 ABSITE Survey data. The dependent variable is an IRT-derived burnout T-score based on 6 survey items corresponding to emotional exhaustion and depersonalization subscales (2019 ABSITE survey items Q15A-Q15F, see §E.1 for details). Program strata refers to program quartile based on program mean 2018 ABSITE burnout T-scores. The 5 th stratum contains programs that had missing 2018 ABSITE data and were thus not ranked in a quartile. However, this stratum dropped out of the adjusted model due to collinearity.			

#### EXHIBIT D.8.B Minimal Detectable Differences for Primary Analysis under Varying Sample Size Scenarios

Number of Programs (Clusters) per Arm	Number of Residents per	Usual Care Mean Burnout	Estimated Intervention	Minimal Detectable Difference	Relative Difference (%)

	Program (Mean Cluster Size)		Mean Burnout		
150	25	45.93	45.26	-0.67	-1.46%
150	20	45.93	45.19	-0.74	-1.61%
150	15	45.93	45.10	-0.83	-1.81%
125	25	45.93	45.19	-0.74	-1.61%
125	20	45.93	45.12	-0.81	-1.76%
125	15	45.93	45.02	-0.91	-1.98%
110	25	45.93	45.14	-0.79	-1.72%
110	20	45.93	45.07	-0.86	-1.87%
110	15	45.93	44.96	-0.97	-2.11%
100	25	45.93	45.10	-0.83	-1.81%
100	20	45.93	45.03	-0.90	-1.96%
100	15	45.93	44.91	-1.02	-2.22%

NOTES: Minimal detectable difference from adjusted estimate of mean burnout scores, assuming mean burnout T-scores in Usual Care=45.933, SD in both arms=9.027, ICC=0.012, alphafinal=0.0443 and power=80%, based on preliminary estimates in EXHIBIT D.8-B. Relative difference is expressed as a percent of Usual Care mean.

#### D.9. STUDY SAMPLE

A total of 209 residency programs enrolled in the SECOND Trial.

Exhibit D.9 shows the distribution of SECOND Trial residency program participants as of November 8, 2019.

**Exhibit D.9. SECOND Trial Sample as of November 8, 2019**

UNIT	Control N	Intervention N	Total N
General Surgery Residency Programs	106	103	209
Mean Burnout T-score a (SD)	50.48 (3.07)	49.98 (3.88)	-
Program Type			
Academic	55	52	107
Community	46	48	94
Military	3	2	5
Mean Number of Residents (SD)	34.08 (16.77)	33.88 (15.95)	-

NOTE: [a] Based on 2019 ABSITE data.

## **D.10. STUDY ARM DESCRIPTIONS**

### **D.10.1. Intervention**

General surgery programs randomized to Intervention will receive:

- Program-specific feedback information on the learning environment as well as resident wellness
- A multi-component Wellness Toolkit of structured interventions for programs to implement to improve their learning environment and resident wellness.

A distinguishing feature of the intervention is that the study team intends to leave it to programs to decide whether and how to act upon the information the Investigators provide. It is the intent of the Investigators to provide information to programs to facilitate appropriate action given a program's specific needs or areas for improvement.

The intervention is expected to be delivered in winter 2019 – 2020.

### **D.10.2. Control**

General surgery residency programs randomized to Control will be expected to conduct “business as usual.” At the behest of Program Directors, Control programs will receive program-specific feedback on resident wellness outcomes (burnout, suicidality, and thoughts of quitting), as well as suicide-related interventions, to ensure that no program will be at a disadvantage with respect to preventing resident suicide.

## **D.11. DATA COLLECTION PROCEDURES**

### **D.11.1. ABS Data**

By enrolling in the FIRST Trial, residency programs agreed to grant the Study Team access to de-identified data from the SECOND Trial Resident Survey ([Appendix 4](#)). The SECOND Study Team designed a brief, closed-ended survey administered annually to all surgical residents taking the January ABSITE; however, the administration of the survey as part of the examination is under the sole purview of the ABS. Data collection and data processing is also executed by the ABS.

The ABS will give the Study Team access to a de-identified dataset containing coded, private information, ABSITE scores, and responses to items in the SECOND Trial Resident Survey Addendum. This de-identified dataset will *not* include any direct personal identifiers (i.e., personal names, addresses, or direct institutional identifiers). The dataset will include analytic identifiers for individual respondents and an analytic institutional identifier to permit appropriate statistical methods for analyzing the data to account for clustering of data. The ABS will also give the Study Team access to a dataset containing program-level ABS Qualifying Examination and Certifying Examination pass rates.

### **D.11.2. Program Wellness Initiatives Inventory Survey**

On April 3, 2019, personalized links to the Program Wellness Initiatives Survey were emailed to all ACGME-accredited general surgery program directors. A reminder was sent to non-responders on June 12, 2019. A reminder to enrollees who had not yet completed the survey was sent following enrollment closing and prior to release of the program-specific report. Completion of the survey is a prerequisite for SECOND Trial enrollment.

The Program Wellness Initiatives Inventory Survey queries program directors about existing activities, resources, education, training, policies, and perceptions of problems ([Appendix 4](#)). It will be distributed via Qualtrics annually to assess what programs, both Control and Intervention, are doing to address well-being.

### **D.11.4. ACGME Data**

ACGME Case Log data and ACGME Annual Resident and Faculty Survey Data will be obtained from the ACGME. The dataset will include an analytic institutional identifier to permit appropriate statistical methods for analyzing the data to account for clustering of data.

### **D. 11.5. ACS NSQIP Data**

The hospital of primarily affiliated with the enrolled residency programs will be asked in 2020 to grant the Study Team access to their hospitals' ACS NSQIP data.

A detailed, official description of the ACS NSQIP data can be found here:  
<http://site.acsnsqip.org/participant-use-data-file/>

### **D.11.6. OTHER DATA**

Hospital-level data from the AHA *Annual Survey of Hospitals* and from CMS *Annual Payment Update Files (PUF)* may be merged at the hospital level to ACS NSQIP data to obtain additional information on hospital characteristics (e.g., bed size, nurse staffing ratios, resident-to-bed ratios, overall case mix index).

## **D.12. STUDY ADHERENCE AND DATA SAFETY MONITORING**

### **D.12.1. Study Adherence**

This is a pragmatic trial. Monitoring to ensure strict adherence to Study Arm conditions will not be undertaken because doing so would threaten the external validity of this study.

However, we will attempt to assess program adherence using the annual Program Wellness Initiatives Inventory Survey (**Appendix 4**) and semi-structured interviews with program directors for the following purposes:

- To undertake “per-protocol” or “as-treated” analyses to estimate the local average treatment effect of increased wellness activities/resources on patient and resident outcomes (to complement our main intent-to-treat analyses)
- To ascertain the demand for personalized data and/or ready-to-implement interventions – i.e., do program directors take advantage of these resources to make targeted changes in their programs?

Adherence may be based on metrics that include but are not limited to:

- Usage of the Wellness Toolkit website
- Completion of the annual Program Wellness Initiatives Inventory Survey
- Implementation of wellness interventions
- Utilization of wellness-intervention implementation support
- Sharing of report data with residents and faculty
- Stability of program leadership
- Buy-in and commitment of program leadership toward improvement of resident well-being and learning environment
- Allocation of resources to intervention implementation

### **D.12.2. Data Safety Monitoring**

#### **D.12.2.1. Data Safety Monitoring Board (DSMB)**

We convened a Data Safety Monitoring Board (DSMB) to independently review study progress at regular intervals. The purpose for establishing a DSMB is to serve as an independent review body to evaluate the results of a planned Interim Analysis that is scheduled for January 2021. The Interim Analysis, described in greater detail in §F.8, will use SECOND Trial Resident Survey data collected from participating programs from 2019 to 2021 to compare resident burnout in programs randomized to Intervention vs. those in programs randomized to Control. The DSMB was charged with determining whether early stopping rules for the SECOND Trial had been met, and if so, to terminate the trial out of consideration for resident wellness.

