#### F.3.1.2. Adjusted Analyses

Covariate adjustment in evaluations of randomized trials is generally done for purposes of increasing statistical efficiency by reducing variance within treatment groups. Covariate adjustment is also sometimes also undertaken on the basis of chance imbalance of baseline characteristics between study groups. Although programs will be randomized to treatment arms in this study, we anticipate considerable variation in the number of ABSITE respondents per program. In the 2019 ABSITE data, the average program had 23 resident respondents (mean=23.11, SD=11.15; coefficient of variation=48%), but the range spanned from a minimum of 3 residents per program to a maximum of 59 residents per program. Such dispersion in cluster sizes may lead to imbalance of resident characteristics

Thus, our analytic approach to evaluating our primary hypothesis will be to estimate a 2-level hierarchical linear model of the general form:

$$y_{ij} = \alpha_0 + \beta_0 TREAT_j + \beta_1 x_{1ij} + \beta_2 x_{2ij} + \cdots + \beta_k x_{kij} + \gamma_1 z_{1j} + \cdots + \gamma_m z_{mj} + \zeta_j + \epsilon_{ij}$$

where  $y_{ij}$  is the burnout T-score of resident  $i$  in program  $j$ ,  $TREAT_j$  is the study arm assignment of program  $j$ , and  $x_{1ij}$ - $x_{kij}$  are resident-level covariates and  $z_{1j}$ - $z_{mj}$  are program-level covariates to be adjusted for, including sampling stratification variables. In this model, under randomization of programs to study arms, the coefficient  $\beta_0$  is the adjusted population-averaged intent-to-treat estimate of the effect of assignment to intervention on mean resident burnout. A coefficient  $\beta_0 < 0$  that is statistically

significant with a one-tailed  $p<0.0443$  provides evidence supporting the effectiveness of the intervention over usual care. Other parameters in the model are the constant ( $\alpha_0$ ), coefficients on other resident-level covariates ( $\beta_1-\beta_k$ ), coefficients on program-level covariates ( $\gamma_1-\gamma_m$ ), program-level random intercepts ( $\zeta_j$ ) and individual-level errors ( $\epsilon_{ij}$ ).

Covariates may include variables listed in §E.3.: resident gender; resident relationship status; resident race; program type; program size; and randomization variables such as the quartile of program  $j$  ranked by 2019 program-level mean burnout scores. This list of covariates is subject to change.

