#### **F.3.3.1. Pre-Post with Control Analyses**

As an additional perspective, we may explore analyses that take baseline rates of programs in each arm into account. In these analyses, rather than identifying the intervention on the basis of a post-only comparison between Intervention and Control, we examine whether *improvement* in outcomes was greater among programs randomized to Intervention relative to improvement in outcomes among programs randomized to Control. These analyses may be executed by regressing pre-post differences in outcomes on study arm assignment and controls for sampling strata as well as other covariates at the discretion of Investigators and analysts, as appropriate to the data. We do not take this approach as our main analytic strategy because the Intervention under investigation is largely untested. Prospective power calculations would require two assumptions: (a) the rate of secular improvement in the absence of the intervention; and (b) the effectiveness of the intervention or its components to estimate the expected difference in mean rates within the Intervention group.

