### **F.5.2. Schedule of Interim Analysis**

The planned Interim Analysis is scheduled for April 2021. This is approximately midpoint through the SECOND Trial Study period, as the first SECOND Trial Resident Survey after dissemination of the Intervention will occur in January 2021.

ACS NSQIP data for the subset of SECOND sites that participate is scheduled to be delivered to the Study Team in January 2021. Because of ACS NSQIP data collection procedures which allow participating hospitals 120 days after the date of a procedure to complete data collection and entry.

A confidential Interim Report will be circulated to DSMB members in May 2021. A DSMB conference call is scheduled for May 2021.

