### **F.5.4. Interim Analysis Statistical Methods**

We expect data for the Interim Analysis to come from the 2021 SECOND Trial Resident Survey. Resident burnout will be measured as previously described in §E.1. We will follow statistical methods that have already described for the analysis of resident burnout, which are outlined in §F.3.1. As discussed in §F.4., the level of statistical significance for the Interim Analysis will be set at  $p_{\text{Interim}} < 0.0056$  to maintain an overall significance level of  $p < 0.05$  for the SECOND Trial as a whole.

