## SECTION H

### STUDY IMPLEMENTATION TIMELINE

In order to successfully implement the SECOND Trial, numerous forms of correspondence with programs need to occur. Correspondence serves as a way to disseminate information to participating hospitals, as well as, for hospitals to provide us with information needed to assure adherence to protocol.

Date	Implementation Activity
1.2.19	First Email for Program Tours Sent
4.3.19	PD Survey Email
4.4.19	Informational Webinar for PDs
4.10.19	Informational Webinar for PDs
4.25.19	APDS Town Hall
6.12.19	PD Survey Reminder Email
6.26.19	Enrollment Email
8.5.19	Enrollment Reminder Email (PDs and Chairs)
8.13.19	Enrollment Reminder Email (DIOs)
8.28.19	Personal Contacts to Unenrolled Programs
8.30.19	Enrollment Deadline Extended
9.4.19	Clarification of Eligibility to NYS Programs
9.30.19	Enrollment Closed
11.2019	Randomization
12.2019	Program Specific Report Delivery
1.2020	Wellness Toolkit Delivery to Intervention
1.2020	SECOND Trial Resident Survey
4.2020	PD Survey
6.2020	Program Specific Report Delivery
1.2021	SECOND Trial Resident Survey
4.2021	PD Survey
5.2021	Interim Report Completed
5.2021	DSMB Conference Call
6.2021	Program Specific Report Delivery
1.2022	SECOND Trial Resident Survey
4.2022	PD Survey
6.2022	Program Specific Report Delivery
1.2023	SECOND Trial Resident Survey
1.2023	Wellness Toolkit Delivery to Control
4.2023	PD Survey
5.2023	Final Report Completed
5.2023	DSMB Conference Call
6.2023	Program Specific Report Delivery

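### D.12.2.1 bases the interim burnout comparison on 2019 to 2021 surveys, F.5.4 on the 2021 survey; pooling the earlier waves as outcomes would dilute the stopping test

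*SAP*

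**What the plan says.** Two sections of the SAP name the data for the same interim test.

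- D.12.2.1 says that the interim analysis "will use SECOND Trial Resident Survey data collected from participating programs from 2019 to 2021 to compare resident burnout" in Intervention and Control programs. It dates the analysis to January 2021 and refers to a section F.8 for detail.
- F.5.4 says: "We expect data for the Interim Analysis to come from the 2021 SECOND Trial Resident Survey". On method it adds: "We will follow statistical methods that have already described for the analysis of resident burnout, which are outlined in §F.3.1".

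Other sections fix the timing and the role of the earlier waves.

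- F.5.2 dates the interim analysis to April 2021 and says that "the first SECOND Trial Resident Survey after dissemination of the Intervention will occur in January 2021".
- D.10.1: "The intervention is expected to be delivered in winter 2019", continuing into 2020. The Section H timeline puts randomization in November 2019, program-specific reports in December 2019, and both "Wellness Toolkit Delivery to Intervention" and a resident survey in January 2020.
- F.3.1.2 lets 2019 burnout into the primary model only through "randomization variables such as the quartile of program", that is, through the randomization strata.
- F.3.3.1 sets the exploratory pre-post analysis apart from the main strategy, describing it as one that works "rather than identifying the intervention on the basis of a post-only comparison between Intervention and Control".

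**The concern.** The interim test feeds the one decision that can end the trial early. Under F.5.3 a statistically significant difference in burnout is a necessary condition for early termination. It is not sufficient, because the DSMB must also find the difference clinically significant and vote to stop. If significance is tested on the wrong waves, the rule may not be met even when the arms truly differ.

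The 2019 responses were given before any program was randomized, so they cannot carry an effect of assignment. The January 2020 responses came about a month after the first reports and in the month the Toolkit went out. On the plan's own account in F.5.2 they are not post-dissemination data. The F.3.1 model has one outcome per resident and no wave or time term. Given 2019 to 2021 data, it would average responses from before and after exposure into one treatment coefficient.

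**Working it through.** **1. The waves against the dates (Section H and F.5.2).**

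| Wave | Position | Can it carry an effect? |
|---|---|---|
| 2019 | before randomization (November 2019) | no |
| January 2020 | after the December 2019 reports, same month as Toolkit delivery | little or none; not post-dissemination by F.5.2 |
| January 2021 | first survey after dissemination | yes |

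**2. The plan's own figures.** The interim level reproduces with O'Brien-Fleming-type spending at half the information and a one-sided total of 0.05: 2(1 − Φ(1.960/√0.5)) = 0.00557, which rounds to the stated 0.0056.

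Exhibit D.8.B, 110 programs per arm with 20 residents each, uses SD 9.027, ICC 0.012, α = 0.0443 and 80% power:

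MDD = SD × √(2(1 + (m − 1)ICC)/(km)) × (z for α/2 + z for power)
= 9.027 × √(2 × 1.228/2200) × (2.011 + 0.842)
= 0.3016 × 2.853 = 0.860, against the stated 0.86.

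The other eleven rows agree to within 0.005.

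**3. Inputs for the interim check.** Programs: 106 Control and 103 Intervention (Exhibit D.9), so 1/106 + 1/103 = 0.01914. Level-2 variance 1.010 and Level-1 variance 81.485 (Exhibit D.8.A, adjusted model). Assumed: 20 respondents per program per wave, equal waves, and a true 2021 difference of 0.86. Critical values at 0.0056 are 2.536 one-sided and 2.770 two-sided. Both are shown because F.3.1.2 is one-tailed, while F.5.3 considers differences in either direction. Power is taken as Φ(difference/SE − critical value).

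**4. 2021 wave only.** SE = 9.027 × √(1.228 × 0.01914/20) = 0.309. Then 0.86/0.309 = 2.779, so power is 60% one-sided and 50% two-sided. Using the variance components instead, SE = √((1.010 + 81.485/20) × 0.01914) = 0.312, and power changes by about one percentage point.

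**5. Waves pooled as outcomes.** The program variance is shared across waves. The resident part depends on overlap. With no overlap it is 81.485/60 for three waves, SE = √((1.010 + 1.358) × 0.01914) = 0.213, and 81.485/40 for two waves, SE 0.242. With the same residents giving the same residual every year it stays at 81.485/20, SE 0.312.

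| Scenario | Observable difference | Power, one-sided | Power, two-sided |
|---|---|---|---|
| 2021 only | 0.86 | 60% | 50% |
| 2019-2021, no effect before 2021 | 0.86/3 = 0.29 | 5-12% | 3-8% |
| 2020-2021, no effect in 2020 | 0.86/2 = 0.43 | 12-23% | 8-16% |
| 2019-2021, half the effect in 2020 | (0 + 0.43 + 0.86)/3 = 0.43 | 12-30% | 8-23% |

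Each range runs from full overlap of residents (low end) to none (high end). The two-sided column applies equally to a harm of the same size.

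**The case against.** The best defence is that D.12.2.1 is a summary. It describes the board's purpose and points elsewhere for detail, and the detailed sections agree with one another: F.5.4 names 2021, F.5.2 explains why, F.3.1 uses 2019 only for strata, and F.3.3.1 treats the main comparison as post-only. No section describes pooling outcome waves, and the missing wave term suggests that F.3.1 was never meant for several waves. One could read D.12.2.1 as 2019 for strata and 2021 for outcome.

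Much of this stands. A reader might infer that the plan intends to pool, but the documents do not say so, and the dilution is therefore conditional. The defence does not remove the conflict: the benign reading gives 2020 no role, and D.12.2.1 says the whole span is used for the comparison between arms.

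Two further points limit the size. Section H first uses the trial's own survey name in January 2020, while the 2019 wave is elsewhere called the ABSITE Survey; on that naming only two waves would pool and the shrinkage is to one half. And because reports went out in December 2019, zero effect in January 2020 is an assumption.

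A reader might also infer from Exhibit D.9 (mean burnout 50.48 in Control, 49.98 in Intervention) that pooling would import a baseline advantage for Intervention and so hide harm. That is not shown. The gap is unadjusted, the stratum terms would absorb part of it, and because program burnout persists from year to year, some of it could also carry into a 2021-only comparison.

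**Conclusion.** The conflict over the interim data source is real and needs no calculation to stand. F.5.2, F.3.3.1 and the Section H dates all support F.5.4, so D.12.2.1 is the section to correct.

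The consequence is conditional on the 2019 to 2021 waves being pooled as outcomes in the F.3.1 model. In that case the observable difference falls to between one third and one half of the true one. Power at a 0.86-point difference falls from about 60% to 5-30% one-sided, or from about 50% to 3-23% two-sided, across all the scenarios tabulated. These figures rest on 20 respondents per program, equal waves, an effect in 2020 of zero or one half, and resident overlap anywhere from none to complete.

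It would go too far to say that the DSMB stops on this test alone, since F.5.3 makes significance only one of its conditions. It would also go too far to carry the point over to the final analysis: the two conflicting statements concern the interim only.

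**What to change.** In D.12.2.1, state that the interim outcome data are the January 2021 resident survey only, as in F.5.4. State that 2019 burnout enters only through the randomization strata or as a baseline covariate, and that the January 2020 wave is not used as outcome data.

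In the same edit, align the interim date in D.12.2.1 (January 2021) with F.5.2 (April 2021), and point the cross-reference to F.5, since Section F ends at F.6 and has no F.8. Any DSMB charter text that repeats the 2019 to 2021 wording should be changed to match.

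The cost is wording only: no change to design, data collection, sample size or significance level.
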